8.4.9 Guidelines for reporting product complaints

Any defect in the IMP must be reported as soon as possible by the Investigator to the monitoring team that will complete a product complaint form within required timelines.

Appropriate information (eg, samples, labels or documents like pictures or photocopies) related to product identification and to the potential deficiencies may need to be gathered. The Investigator will assess whether or not the quality issue has to be reported together with an AE or SAE.

8.5 TREATMENT OF OVERDOSE

Sponsor does not recommend specific treatment for an overdose.

In the event of an overdose, the Investigator should:

1. Contact the Medical Monitor immediately.
2. Closely monitor the participant for any AE/SAE and laboratory abnormalities until dupilumab can no longer be detected systemically (at least 28 days).
3. Document appropriately in the CRF.

Decisions regarding dose interruptions or modifications will be made by the Investigator in consultation with the Medical Monitor based on the clinical evaluation of the participant.

8.6 PHARMACOKINETICS

PK parameters are not evaluated in this study.

8.7 PHARMACODYNAMICS

Pharmacodynamics is evaluated using TEWL assessments as described [Section 8.2.1](#).

8.8 GENETICS

A blood sample for DNA isolation will be collected at baseline from all participants for filaggrin gene sequencing analysis. Blood for DNA isolation should be collected on Day 1/Baseline (pre-dose) but may be collected at any study visit.

Participants who provide a blood sample may agree to broader genetic analysis, in addition to the mandatory filaggrin gene sequencing analysis. Optional broad genetic analysis may include, but is not limited to, whole exome or whole genome sequencing. Participants will be required to separately agree to this optional genetic research within the informed consent form (ICF) to consent to broad genetic analysis. Participants who do not wish to participate in optional broad genetic research may still participate in the study.

In the event of DNA isolation failure, a replacement genetic blood sample may be requested from the participant. Signed informed consent will be required to obtain a replacement sample unless replacement collection was included in the original consent.

Details on processes for collection, storage, shipment and destruction of these samples can be found in the study reference manual. See Appendix ([Section 10.5](#)) for information regarding genetic research.

DNA samples may be stored for a maximum of 15 years following the last participant's last visit for the study at a facility selected by the Sponsor.

8.9 BIOMARKERS

Collection of serum, plasma and skin samples for potential, future biomarker research is also part of this study.

8.9.1 Lipidomics assessment

Samples for skin lipidomic assessment are required and will be collected from all participants in this study as specified in the SoA ([Section 1.3](#) and [Section 1.4](#)).

Targeted skin lipidomics will be performed by means of a validated mass spectrometry method from skin tapes that have been collected during tape stripping at the TEWL assessment.

Lipidomics in skin will be assessed in skin tapes from skin tapes obtained from lesional skin, non-lesional skin and normal skin.

Skin tape strip samples may be stored for a maximum of 5 years following the last participant's last visit for the study at a facility selected by the Sponsor.

8.9.1.1 Filaggrin breakdown products

Filaggrin is a structural protein that plays an important role in controlling water retention in the skin, and the hygroscopic properties of FLG breakdown products have an important role as natural moisturizing factor ingredients (31). Filaggrin deficiency leads to impaired lipid profile and altered acidification pathways (32). Lipid abnormalities have been reported in patients with FLG mutations (33).

Filaggrin breakdown products, cis/trans-urocanic acid (total UCA) and pyrrolidone carboxylic acid (PCA), also known as pyroglutamic acid, will be quantified via a liquid chromatography electrospray ionization tandem mass spectrometry (LC-ESI-MS/MS) approach in the same tape strips that are used for lipidomics assessment.

8.9.1.2 Analysis of stratum corneum lipids

It has been reported that lesional and non-lesional skin of AD patients has decreased EOS ceramides and other ceramides with very long-chain fatty acids (C22–C30), and increased short-chain fatty acids NS CER (C16–C20) (12). Highly hydrophobic ω -esterified acid sphingosine ceramides (EOS CER) and NS CER will be analyzed as follows.

STS processing for lipid extraction

STS will be processed through a Bligh and Dyer procedure as previously described (12). The bottom chloroform layer from the skin tape extraction will be used for lipid analyses while upper water-methanol phase will be used for polar component analyses by the LC-MS/MS. A fixed amount of internal standards (N-palmitoyl-D-erythro-sphingosine (d7), (d7)NS CER and d18:1/26:0/18:1(d9) or (d9)EOS CER) will be added at the beginning of the extraction process. Protein interphase formed during extraction process will be hydrolyzed with 1N NaOH (80°C x 3h), neutralized with 1N HCl and protein content will be measured using BCA (bicinchonic acid) protein assay. All mass spectrometric data will be normalized to the total amount of hydrolyzed protein determined as described above.

EOS CER and NS CER will be identified and quantified using a targeted UHPLC-ESI-MS/MS.

8.9.1.3 Quantification of protein bound ceramides

Protein bound ceramides are formed from EOS CER and represent a portion of EOS CER without linoleic acid and thus having a terminal hydroxy group in N-linked fatty acid. Protein-bound ceramides are released from proteins during protein hydrolysis procedure (see above). Therefore, after protein determination in hydrolysates, freed omega-OH ceramides will be extracted using Bligh and Dyer procedure as described above with the addition of fixed amount of (d7)NS CER to ensure ceramide quantitation. Omega hydroxy fatty acid containing ceramides will be detected by the UHPLC-ESI-MS/MS as described above using appropriate transitions from corresponding molecular ions to the m/z 264, 292, and 320. As most standards of omega hydroxy fatty acid containing ceramides are not available, quantitation will be performed against standard curves of NS-ceramides. Obtained values will be normalized against protein content in the samples.

Detailed guidelines and requirements for samples preparation, handling of skin tapes after stripping, storage and shipment of such skin tapes will be provided in the study reference manual.

8.9.2 Proteomics

Proteomics in skin will be assessed in skin tapes obtained from lesional skin, non-lesional skin and normal skin.

Protein extracts will be prepared from STS samples by LC-MS/MS.

The following 3 major functional groups of proteins associated with skin barrier function will be examined:

- Keratin intermediate filaments
- Proteins associated with inflammatory response (S100 proteins, alarmins, protease inhibitors)
- Glycolysis and oxidative stress response proteins (glycolytic enzymes, oxidative stress response enzymes)

Skin proteomics samples may be stored for a maximum of 5 years following the last participant's last visit in the study at a facility selected by the Sponsor.

Detailed sample preparation for proteomic analysis will be provided in a separate study reference manual.

8.9.3 Transcriptomics

Transcriptomics in skin will be assessed in skin tapes obtained from lesional skin, non-lesional skin and normal skin.

Skin tapes will be collected and stabilized in RLT buffer with DTT and stored frozen at -80°C for transcriptomic analysis. Skin tape transcriptome samples will be shipped to National Jewish Health, where total RNA will be isolated and RNA sequencing will be performed using qualified methods (10, 17) to support whole transcriptome analysis and data generation.

Skin transcriptomics samples and any RNA isolated from the samples may be stored for a maximum of 5 years following the last participant's last visit in the study at a facility selected by the Sponsor.

Transcriptome sample preparation and analysis details will be provided in a separate study reference manual.

8.9.4 Optional samples for biomarker research

Optional serum and plasma samples for biomarker research that should be collected from participants in the study, where possible, are the following:

- Venous blood samples will be collected at baseline and end of treatment/end of observation at Week 16 to obtain serum and plasma to be stored for possible future research related to response, disease activity, safety, the Type 2 inflammation pathway, and for assessing the effects of the study drug on modulation of IL-4 receptor and on atopic disease processes, as well as to study biomarkers that may have predictive utility for response to dupilumab treatment.
- The results of exploratory research testing will not be included in this CSR.

Details on collection, storage and shipment of these samples will be provided in the study reference manual.

Plasma and serum samples may be stored for a maximum of 5 years following the last participant's last visit for the study at a facility selected by the Sponsor.

8.10 IMMUNOGENICITY ASSESSMENTS

No antibodies to dupilumab will be evaluated in this study.

8.11 HEALTH ECONOMICS

Not applicable.

9 STATISTICAL CONSIDERATIONS

The material in Section 9 of the clinical trial protocol constitutes the statistical analysis plan for the study. However, biomarkers' analyses: ie, lipidomics, proteomics, transcriptomics, and filaggrin genotyping, will be detailed in a specific statistical analysis plan. If the statistical analysis plan in the present document needs revision during the study to provide further details or adapt to unexpected issues in study execution and data that affect planned analyses, a statistical analysis plan or an appropriate statistical technical document (STD) reflecting the changes will be issued prior to database lock or any interim analysis.

If no major adaptation to the statistical analysis planned in the present document is needed, a STD will be issued to document only technical conventions used for the analyses (and minor modifications from the planned analyses, if any).

The following definitions will be used in Section 9:

- Cohort: the study includes two cohorts: patients with moderate to severe AD cohort and healthy volunteers cohort.
- Group: three groups are identified: patients' lesional skin area group, patients' non-lesional skin area group and healthy volunteers' normal skin group.

9.1 STATISTICAL HYPOTHESES

No hypothesis testing is predefined in this exploratory study.

9.2 SAMPLE SIZE DETERMINATION

Sample size for this exploratory study was based on medical/clinical judgement and is consistent with the sample size from similar studies in the literature (1). No formal sample size calculation was performed. TEWL data collected in similar settings as planned for this study were not available: ie, TEWL values after 5 skin tape strips, and pre- and post-dupilumab treatment are unknown.

Allowing for drop-out rate of 15%, a total of approximately 24 patients with moderate to severe AD will be enrolled to achieve 20 evaluable patients: ie, patients with no major or critical deviations related to IMP and/or TEWL measurements, for whom the TEWL data for primary analysis: ie, TEWL at baseline and Week16, are considered sufficient and interpretable. An approximately equal number of age, gender, location of targeted lesion area and site matched healthy volunteers serving as a reference comparator cohort will be enrolled. Drop-out rate in healthy volunteers is expected to be zero. Any drop-out healthy volunteer for whom the matched patient is considered as evaluable will not be replaced.

9.3 POPULATIONS FOR ANALYSES

For purposes of analysis, the following populations are defined ([Table 3](#)):

Table 3 - Populations for analyses

Population	Description
Enrolled	All participants who sign the ICF
Intent-to-treat (ITT)	The ITT population includes all enrolled patients, who received at least one dose of IMP and all enrolled healthy volunteers who have at least one TEWL/STS assessment performed, irrespective of compliance with the study protocol and procedures.
Modified Intent-to-treat (mITT)	The mITT population includes all ITT participants. If prohibited therapies for AD (see Section 6.5.1) are used and assessed by the study team as having a significant impact on skin barrier only visits prior to rescue treatment use are considered.
Efficacy	The mITT and ITT populations
Safety	The safety population includes all patients, who actually received at least one dose of IMP or had at least one TEWL/STS assessment and all healthy volunteers who have at least one TEWL/STS assessment performed.

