Within the targeted skin area of healthy volunteers -the predefined skin location for TEWL and STS must be identical to the lesional area of the patient to which a healthy volunteer is matched- three closely adjacent spots without an overlap for the skin tapes will be identified for subsequent skin barrier function assessment.

The skin barrier function without and before STS will be assessed using TEWL measurement on each of the three spots at each visit.

On normal skin in healthy volunteers at each visit at baseline, Week 2, Week 4, Week 8, Week 12, and Week 16, TEWL will be measured before and after 5, 10, 15, and 20 STS on the predefined first, second or third spot respectively for skin barrier function assessment (5 TEWL assessments per visit in normal skin) at the same location as for the lesional skin in the matching AD patient and as described above.

In particular, STS assessment on baseline (Week 0, Day 1), Week 8 (Day 57) and Week 16 (Day 113) will be conducted on the first spot within the location-matched, normal skin. STS assessment on Week 2 (Day 15) will be conducted on the second spot. STS assessment on Week 4 (Day 29) and Week 12 (Day 85) will be conducted on the third spot.

Study drug will be administered on-site by study site staff at baseline, Week 2, 4, 6, 8 and Week 12, after the TEWL assessment has been completed. Study drug will be self-administered at home by AD patients at Week 10 and 14.

Intervention groups and duration:

This is a 16-week, open-label study of dupilumab in moderate to severe AD patients. Age-, gender-, targeted lesion area- and study-site-matched healthy volunteers will be included for a non-treatment, 16-week evaluation period. Total study duration including screening and follow-up phone call will be 24 weeks.

Study intervention(s)

Investigational medicinal product(s)

Dupilumab 200 mg

- Formulation: a 175 mg/mL dupilumab solution in a pre-filled syringe to deliver 200 mg in a 1.14 mL subcutaneous injection.
- Route(s) of administration: subcutaneous injection (SC).

Dupilumab 300 mg

- Formulation: a 150 mg/mL dupilumab solution in a pre-filled syringe to deliver 300 mg in a 2 mL subcutaneous injection.
- Route(s) of administration: subcutaneous injection (SC).
- Dose regimen

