- Evolution over time of TEWL before STS and TEWL AUC by type of skin area will be analyzed. Matched healthy subjects will provide normal reference values.
- **Safety/other analysis:**
 - The safety evaluation will be conducted on all AD patients who receive at least one dose of dupilumab or had at least one TEWL/STS assessment performed, and on all healthy volunteers, who had at least one TEWL/STS assessment. The analysis will be based on descriptive statistics providing summary statistics for vital signs parameters (including summary of Potentially Clinically Significant Abnormalities (PCSAs)) and reported adverse event.

Data Monitoring Committee: None

[figure not shown]

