			D4 ±2 days	D8 ±2 days	D11 ±2 days	D15 ±2 days	D22 ±2 days	D29 ±2 days	D43 ±2 days	D57 ±3 days	D85 ±3 days				
Day	D-28 to D-1	D 1												UNSCH	
Week		W0	W1			W2	W3	W4	W6	W8	W12	W16	W20		
Visits	V01	V02	V03	V04	V05	V06	V07	V08	V09	V10	V11	V12	V13		
Quality of sleep NRS ^g		X	X	X	X	X	X	X	X	X	X	X		(X)	X
Safety															
Adverse event collection	X	X	X	X	X	X	X	X	X	X	X	X	X	X	X
Height		X													
Body weight		X										X			X
Vital signs ^d	X	X								X		X		(X)	X
Physical examination	X	X ^k										X ^k			X ^k
Pregnancy test (urine), WOCBP only ^e	X	X						X		X	X	X			
DNA sampling for filaggrin gene sequencing		X													
Optional assessments															
DNA sampling for future research		X													
Biomarker research samples (serum and plasma)		X										X			X

a EoS safety follow-up by phone.

b Loading dose dupilumab arm 600 mg (300 mg x 2 ie, two 300 mg syringes) for all adult patients and for those adolescents weighing 60 kg and above, and 400 mg (200 mg x 2 ie. two 200 mg syringes) for adolescent patients below 60 kg, followed by bi-weekly SC dosing of 300 mg dupilumab to adults and adolescents weighing 60 kg and above and bi-weekly SC dosing of 200 mg to adolescents weighing below 60 kg. Dupilumab administration on following days: D1 (V02,W0) baseline, D15±2days (V06, W2), D29±2days (V08, W4), D43±2days (V09, W6), D57±3days (V10, W8), D71±3days (W10; self-administration of dupilumab at home), D85±3days V11, W12), D99±3days (W14; self-administration of dupilumab at home).

c Assessments on treatment days are to be conducted before administration of dupilumab.

d Vital signs, including systolic and diastolic blood pressure (mmHg), pulse rate (beats per minute), body temperature (°C), and respiratory rate will be measured at Screening, Baseline at Week 0, Week 8, and Week 16 (EoT). Height (cm) will be measured at Baseline only. Body weight (kg) will be measured at Baseline, and Week 16 (EoT).

e Only for women of childbearing potential. Pregnancy will lead to definitive treatment discontinuation in all cases.

f DLQI will be used for adults; CDLQI will be used for adolescents.

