9.4.5 Extent of study treatment exposure and compliance

The extent of study treatment exposure and compliance will be assessed and summarized for patients' cohort within the safety population.

The following listings will be provided:

- Patients receiving IMP from specified batch; (patient, drug product batch number, drug product) will be sorted by patient.

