9.4.8.1 Adverse events

9.4.8.1.1 Definitions

Adverse events will be coded to a "Preferred Term (PT)" and "High Level Group Term (HLGT)", "High Level Term (HLT)" and primary "System Organ Class (SOC)" using the Medical Dictionary for Regulatory Activities (MedDRA, version currently in use by the sponsor at the time of database lock).

For patients' cohort, they will be classified into predefined standard categories according to chronological criteria:

- Pre-treatment AEs: AEs that occurred, worsened or became serious during the pre-treatment period defined as the time between informed consent signature and the first IMP administration.

- Treatment emergent AEs (TEAEs): AEs that occurred, worsened or became serious during the TEAE period defined as the time from the first IMP administration up to the end of treatment visit (EoT included).
- Post-TEAEs: AEs that occurred, worsened or became serious during the post-TEAE period defined as the time starting after the TEAE period.

TEAEs will be assigned to the treatment received at the time of the AE onset.

If the onset date (or time) of an AE (occurrence, worsening or becoming serious) is incomplete or missing, then the AE will be considered as a TEAE unless a partial date (or time) shows it as a pre- or post-treatment event.

For all healthy volunteers, safety data will be considered as part of a single period starting with the signature of the informed consent and ending with the end of study visit (EoS included).

All AEs reported in the study will be listed, sorted by subject/patient, onset date and time.

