9.4.8.1.2 Treatment-emergent adverse events

The following TEAEs summaries will be provided for the patients' cohort of the safety population:

Overview of TEAEs: number and percentage of subjects with any TEAE, any serious TEAE, any TEAE leading to death (if any occurred), any TEAE leading to permanent treatment discontinuation, and any TEAE of special interest.

- Summary of TEAEs by primary SOC and PT:
 - Number and percentage of patients with at least one TEAE;
 - Number of occurrences of TEAEs.

Patients presenting TEAEs will be listed sorted by primary SOC and PT. By definition, no TEAEs summary will be displayed for healthy volunteers.

AEs that occur outside the treatment emergent period or in healthy volunteers will be summarized separately.

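### The safety population's 'or TEWL/STS' clause would put any AD patient assessed on Day 1 but never dosed into the TEAE and AESI denominators, with no treatment-emergent time at risk

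*Protocol*

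**What the plan says.** - **Who is in the safety set.** Protocol 9.3, Table 3: "The safety population includes all patients, who actually received at least one dose of IMP or had at least one TEWL/STS assessment". The synopsis (1.1) gives the same rule: "all AD patients who receive at least one dose of dupilumab or had at least one TEWL/STS assessment performed".
- **Contrast with ITT.** The same table requires a dose: "The ITT population includes all enrolled patients, who received at least one dose of IMP".
- **Order on Day 1.** The synopsis has the study drug given "after the TEWL assessment has been completed". Footnote c of the AD schedule (1.3) agrees: "Assessments on treatment days are to be conducted before administration of dupilumab".
- **When a TEAE can start.** Under 9.4.8.1.1 the TEAE period is "defined as the time from the first IMP administration up to the end of treatment visit (EoT included".
- **Where the set is used.** Section 9.4.8 applies the safety population to all safety analyses. Section 9.4.8.1.2 asks, for the patients' cohort of that population, for an "Overview of TEAEs: number and percentage of subjects with any TEAE", and 9.4.8.1.5 asks for number (%) with treatment-emergent AESI. Section 9.4.8.2 counts patients with vital-sign PCSAs during the TEAE period. Section 9.4.5 uses the same cohort for exposure and compliance: "The extent of study treatment exposure and compliance will be assessed and summarized".
- **SAP.** Section 1.2 modifies the mITT population and adds AE summaries by cohort and age group. It leaves the safety population as the protocol has it.

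**The concern.** A treatment-emergent incidence should have in its denominator the people who could contribute such an event. For AD patients, the second condition of the safety definition works only when the first fails, that is, when no dose was given. The only people it can add have no treatment-emergent time. Neither document names a dosed-only subset for the TEAE or AESI tables.

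At stake is the accuracy of the trial's main safety percentages. The cohort is small, and the SAP divides the AE summaries further by age group, so one extra person in a denominator is visible. A second, smaller matter is that the individual exposure and compliance formulas need dose dates that an undosed patient does not have.

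**Working it through.** **1. Cohort size.** Protocol 9.2 plans for 20 evaluable patients with 15% drop-out: 20 / (1 − 0.15) = 23.5, rounded up to 24. This reproduces the stated figure. The synopsis caps each age group at 12.

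**2. Who the second condition adds.** Let A = dosed and B = at least one TEWL/STS assessment. The safety set is A or B. Anyone in A is already in, so B adds only patients in B and not in A. Because assessment comes before injection on Day 1, a patient who stops between the two falls there. That patient is in the safety set but not in ITT.

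**3. Effect on a TEAE or AESI percentage.** Let N be the AD patients in the safety set, u the undosed among them, and x the number with a TEAE, all in dosed patients.

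- As planned: x / N
- In dosed patients: x / (N − u)
- Ratio: (N − u) / N, so the relative understatement is u / N

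The documents give neither u nor x. The values of u below, and the 50% planned rate used for illustration, are assumptions.

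| N | u | Ratio | Relative understatement | Example: planned vs dosed only |
|---|---|---|---|---|
| 24 | 0 | 24/24 | 0% | 12/24 = 50.0%, no change |
| 24 | 1 | 23/24 | 4.2% | 12/24 = 50.0% vs 12/23 = 52.2% |
| 24 | 2 | 22/24 | 8.3% | 12/24 = 50.0% vs 12/22 = 54.5% |
| 12 | 1 | 11/12 | 8.3% | 6/12 = 50.0% vs 6/11 = 54.5% |
| 12 | 2 | 10/12 | 16.7% | 6/12 = 50.0% vs 6/10 = 60.0% |

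If the undosed patient came on top of 24 dosed patients, the understatement would be 1/25 = 4.0%. SAP 1.2 reports an imbalance between adults and adolescents. The smaller group may therefore have fewer than 12, which makes u/N larger.

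**4. Exposure and compliance.** Exposure (9.4.5.1) is last dose date minus first dose date plus 14 days. The fallback to a dispensing date replaces only an unknown last date, so an undosed patient has no value. Compliance (9.4.5.2) divides by administrations planned up to the last administration date, which also does not exist. However, 9.4.5.2 rules out imputation, and SAP 1.3 has quantitative summaries report the number of observations. Means and medians therefore rest on patients who have values. What remains open is the denominator of the categorical percentages, such as compliance below 80% and the under-planned dosing bands.

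**5. One exception on events.** Under 9.4.8.1.1 an AE with missing onset is a TEAE unless a partial date shows otherwise, so on that wording an undosed patient could be given one. SAP 1.3 also allows other information to rule it out, and absence of dosing should do so.

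**The case against.** **It may never happen.** Stripping and injection fall in the same visit, after screening and with eligibility rechecked on Day 1. The 15% drop-out covers loss of evaluability up to Week 16, so it is no estimate of undosed patients. This stands: the point is conditional.

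**The shift is small.** The exact 95% interval for 12/24 is 29.1% to 70.9%, which easily contains 52.2% and 54.5%. Safety is descriptive, and TEAEs are not tabulated for healthy volunteers, so no planned between-group comparison changes. This stands, and it limits the importance. It does not make the denominator right.

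**The wide set has a purpose.** It appears in both the synopsis and Table 3, matches the healthy-volunteer criterion, and captures reactions to stripping, whose risks Protocol 2.3.1 lists. This is a good reason to keep it for those events. In undosed patients they fall outside the TEAE period, and 9.4.8.1.2 already summarises such events separately. They do not need undosed patients in the TEAE denominator.

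**A reader could recompute.** Counts by population are reported (9.4.1.1, 9.4.3), ITT is the dosed set for AD patients, and TEAE tables give numbers as well as percentages. This holds for the whole cohort. Neither section promises population counts by age group, where the effect is larger.

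**A stronger reading on exposure and compliance.** A reader might infer that these summaries are diluted like the TEAE rates, or become undefined. The documents do not support that: only the undosed patient's own value is undefined, and the cohort summaries can still be computed.

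**Conclusion.** The point holds in conditional form. In the only case where the TEWL/STS condition operates for AD patients, it adds people without treatment-emergent time to the TEAE and AESI denominators, and the SAP does not correct this. The size is u/N. Assuming one undosed patient, that is 4.2% relative among 24 and 8.3% in an age group of 12; it is zero if all assessed patients are dosed. A reader might infer that the reported rates will in fact be understated, but nothing in the documents shows that any patient was or will be assessed and left undosed. For exposure and compliance the defect is limited to an unstated denominator for categorical percentages. The TEAE-period PCSA counts raise the same denominator question if percentages are attached to them. This is a modest specification gap, worth closing because closing it is simple.

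**What to change.** State in the SAP that, for AD patients, the TEAE, AESI, exposure, compliance and TEAE-period vital-sign PCSA summaries, overall and by age group where AE summaries are split, use patients with at least one dose of IMP, that is, the patients of the ITT set. Keep the wider dose-or-TEWL/STS set for AE listings and for the separate summary of AEs outside the treatment-emergent period, including stripping reactions in undosed patients. An undated AE in an undosed patient then goes to that separate summary and cannot be counted as a TEAE.

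The cost is wording, plus a filter on a population flag that the plan already defines. No data collection changes. Protocol Section 9 already provides for a technical document recording minor modifications, so the change can be made there before database lock.
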